#### Reporting in eCRF

It will be recorded in the eCRF if an ECG was performed and, if applicable, the investigator's assessment of ECG results ('normal', 'abnormal, not clinically significant', 'abnormal, clinically significant'). If an ECG was not performed, a reason should be given.

Any new clinically significant abnormal finding at the baseline visit will be recorded as an AE in the parent trial. Any clinically significant deterioration of a pre-existing condition recorded in the parent trial, as well as any new clinically significant sign, symptom, or illness occurring after the baseline visit will be recorded as an AE in accordance with Section 13.3.

Page 61 of 121

## 11.5.4 Assessment of local tolerability

Subjects and investigators will each provide an assessment of local tolerability according to the schedule of trial procedures (Section 4).

While on treatment, the subject will complete a daily assessment of stinging/burning in connection with the IMP applications in the eDiary. The subject will be asked to retrospectively assess the worst stinging/burning in connection with the IMP application during the day. The assessment will be done using the 4-point scale shown in Panel 13.

Panel 13: Subject assessment of local tolerability after IMP application

Grade (severity)	Stinging/burning		
0 (none)	No stinging or burning.		
1 (mild)	Slight warm, tingling sensation, not really bothersome.		
2 (moderate)	Definitive warm, tingling sensation, that is somewhat bothersome.		
3 (severe)	Hot, tingling/stinging sensation that has caused definite discomfort.		

**Abbreviation:** IMP = investigational medicinal product.

While the subject is on treatment, the investigator will assess whether he/she suspects a local skin reaction related to application of the IMP. If the investigator suspects a local skin reaction related to application of the IMP, the skin reaction will be scored according to the Berger and Bowman scales in Panel 14. The scoring should only assess skin signs suspected to be related to application of the IMP and not signs or symptoms related to the subject's CHE.

Following scoring according to the Berger and Bowman scales, an IMP patch test will be performed to confirm a possible diagnosis of allergic contact dermatitis caused by the IMP, see procedure described in Section 11.5.4.1. The aetiology of the local skin reaction will be captured in the eCRF and the final diagnosis will be captured as an AE.

The subject's assessment of local tolerability may be reported as an AE at the discretion of the investigator, even if the investigator does not suspect a local skin reaction related to application of IMP (reporting of e.g. pain or stinging/burning by the subject).

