- 8. AEs occurring at or prior to baseline visit in this extension trial should be recorded in the parent trial. If ongoing at baseline visit for this extension trial, the AE will be recorded as medical history in the extension trial.
- 9. If the subject has IGA-CHE ≥2, delgocitinib 20 mg/g will be dispensed.
- 10. Before the first application of delgocitinib cream 20 mg/g and each time treatment is re-initiated, the subject will be instructed on how much cream to apply and which area(s) to treat.
- 11. If the subject has IGA-CHE ≥2, subject will apply delgocitinib cream 20 mg/g twice daily until IGA-CHE 0 (clear) or 1 (almost clear) is achieved.
- 12. Treatment application (yes/no) will be recorded daily by the subject in the eDiary from Day 1 onwards up to end of treatment/early termination.
- 13. All returned, opened delgocitinib cream 20 mg/g tubes will be weighed at site. Subjects must return all previously dispensed tubes of delgocitinib cream 20 mg/g to the site at all visits (scheduled and unscheduled).
- 14. HESD eDiary data from the parent trial starting from 1 week prior to and until Day 1 (baseline) in this extension trial will be transferred and considered as data for this extension trial.
- 15. While on treatment with delgocitinib cream 20 mg/g, local tolerability will be evaluated daily by the subject in the eDiary.
- 16. Subjects do not have to be fasting for safety laboratory samples.
- 17. For women of childbearing potential, a urine pregnancy test must be performed at each scheduled visit.
- 18. It will be at the investigator's discretion to decide whether a urine sample should be sent to the central laboratory for further analysis.
- 19. Only to be performed if the subject is on treatment with delgocitinib cream 20 mg/g.
- 20. Only applicable if the subject is on treatment with delgocitinib cream 20 mg/g and if the investigator suspects contact dermatitis based on the initial inspection of the subject's hands and the subject's assessment of local tolerability (Section 11.5.4).

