# 9.2 Administration of investigational medicinal products

Delgocitinib cream 20 mg/g will be administered as a twice-daily topical application, as needed (see Section 7.1). The applications will be performed approximately 12 hours apart. Instructions for use will also be provided.

Delgocitinib cream 20 mg/g will be applied to clean, dry hands, fingers, fingertips, and wrists in a thin layer covering the affected areas. The amount of delgocitinib cream 20 mg/g to be used depends on the size of the affected area and the size of the hands, fingers, fingertips, and wrists. 1 tube of 15 g delgocitinib cream is considered sufficient for treatment of the whole surface of the hands, fingers, fingertips, and wrists twice daily for 1 week; however, a few patients may need more (based on experience from the LP0133-1273 trial), which will be allowed at the discretion of the investigator.

Page 42 of 121

Prior to the first application of delgocitinib cream 20 mg/g and each time treatment is re-initiated, the subject will be instructed on how much cream to apply and which area(s) to treat.

Only the affected area(s) on the hand(s), finger(s), fingertip(s), and wrist(s) will be treated. If new CHE lesions occur on initially untreated area(s) of the hand(s), finger(s), fingertip(s), and wrist(s), these new lesions will be treated with delgocitinib cream 20 mg/g as well.

At the scheduled trial visits, investigator assessments of efficacy should preferably be done at least 2 hours after application of delgocitinib cream 20 mg/g or emollient. Recommendations for bathing, washing, and hand sanitising in relation to delgocitinib cream 20 mg/g application are provided in Section 9.6.

Tubes of delgocitinib cream 20 mg/g will be dispensed by the investigational staff if it is decided during a visit (scheduled or unscheduled) that a subject should start treatment. After that, delgocitinib cream 20 mg/g tubes will be dispensed to the subject at each scheduled visit until it is decided that the subject should stop treatment. Application of delgocitinib cream 20 mg/g will be recorded by the subjects each day in the eDiary.

Returned opened tubes of delgocitinib cream 20 mg/g will be weighed at the trial site to determine the amount of cream used. Subjects must return all previously dispensed tubes of delgocitinib cream 20 mg/g to the site at all visits (scheduled and unscheduled). For details on handling of unopened tubes, see Section 9.8.3.

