## 11.3 eDiary assessments

Subjects participating in this extension trial will have their eDiary set up for the extension trial by the trial site staff. Daily completion of the eDiary will continue in this extension trial.

At the baseline visit, the subjects will have their eDiary device updated. The eDiary will be open for entry from 4 pm until midnight. HESD eDiary data from the parent trial starting from 1 week prior to and until Day 1 (baseline) in this extension trial will be rolled over. The Hand Eczema Symptom Diary (HESD) must be completed in the eDiary every evening until Week 36. Treatment application (daily) and subject assessment of local tolerability (daily while on treatment) will be evaluated by the subject in the eDiary from baseline up to end-of-treatment/early termination. Compliance with the eDiary completion will be reviewed by the trial site staff throughout the trial.

Update, training, and return of the eDiary are outlined in the schedule of trial procedures (Section 4).

The following assessments will be completed in the eDiary by the subjects in the listed order:

- Daily: HESD (see Section 11.4.3.2).
- Daily: treatment application (see Section 9.8.4).
- Daily while on treatment: subject assessment of local tolerability (see Section 11.5.4).

Page 55 of 121

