## 11.4.3.2 Hand Eczema Symptom Diary (HESD)

The HESD is an instrument used in the phase 2b trial with delgocitinib (LP0133-1273) and has been further revised for use in the parent trials and this extension trial. The HESD is a 6-item PRO instrument designed to assess severity of CHE signs and symptoms. Subjects will assess the worst severity of 6 individual signs and symptoms of CHE (itch, pain, cracking, redness, dryness, and flaking) over the past 24 hours using an 11-point numeric rating scale with anchors of 0='no (symptom)' and 10='severe (symptom)'. The HESD score is derived as an average of the 6 items. Subjects will complete the HESD as an eDiary each evening from Week 0 until Week 36 (see Section 4).

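### The once-daily tolerability item covers only the same day and can be answered before the evening application, so reactions to that application can be missing from the diary

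*Combined protocol and SAP*

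**What the plan says.** Four statements bear on the point.

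- **What is asked (Section 11.5.4).** One rating per day while on treatment, meant to cover both applications: "While on treatment, the subject will complete a daily assessment of stinging/burning in connection with the IMP applications in the eDiary". The recall period is the current day: "The subject will be asked to retrospectively assess the worst stinging/burning in connection with the IMP application during the day". Panel 2, footnote 15, repeats the daily frequency without a recall period.
- **When it can be answered (Section 11.3).** "The eDiary will be open for entry from 4 pm until midnight". The only further timing instruction concerns the symptom diary: "The Hand Eczema Symptom Diary (HESD) must be completed in the eDiary every evening until Week 36". The tolerability item comes last in the listed order and has no timing rule of its own.
- **When cream is applied (Section 9.2).** "The applications will be performed approximately 12 hours apart". No clock times are given.
- **The contrast (Section 11.4.3.2).** The HESD, in the same diary, asks for worst severity "over the past 24 hours using an 11-point numeric rating scale".

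Section 14.3.9 summarises the item by nominal week. Section 13.2 has tolerability queried at visits and reported as an AE where the investigator finds it relevant.

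**The concern.** An assessment of the day's worst reaction should follow the events it rates. Here it may precede one of the two. If a subject answers at 5 pm and applies cream at 8 pm, that day's entry cannot rate the 8 pm application. The next day's entry, as described, asks about the next day.

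The item matters because the primary objective is long-term safety, and Section 5.5 names burning and stinging among the local reactions to be expected with a topical product. It also has uses beyond a summary table. Under Panel 2, footnote 20, the subject's rating is part of the basis for suspecting contact dermatitis, which leads to scoring and patch testing. Under Section 11.5.4 it may become an AE. Subjects who had vehicle in the parent trial and enter with IGA-CHE of 2 or more meet delgocitinib for the first time in this trial, so their first application is of particular interest.

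**Working it through.** The plan states no figure to reproduce. The check is clock arithmetic.

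**Inputs from the documents:** entry window 16:00 to 24:00, 8 hours (11.3); about 12 hours between applications (9.2); one entry per day with same-day recall (11.5.4).

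**Input not in the documents:** the time of the first application, t1, assumed to be 06:00 to 09:00.

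**Step 1. Can the entry precede the second application?** The second application is at t2 = t1 + 12 h. The diary is already open for t2 − 16 = t1 − 4 hours by then, which is positive whenever the first application is later than 04:00.

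| t1 (assumed) | t2 | Hours open before t2 | Share of 8 h window |
|---|---|---|---|
| 06:00 | 18:00 | 2 | 25% |
| 07:00 | 19:00 | 3 | 37.5% |
| 08:00 | 20:00 | 4 | 50% |
| 09:00 | 21:00 | 5 | 62.5% |

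**Step 2. Share of applications unrated.** Let p be the proportion of on-treatment days on which the entry precedes t2. On such a day one of two applications is unrated, so the share is p × 1/2. With p = 0 it is 0%; with p = 1 it is 50%. The documents do not allow p to be estimated. Purely as illustration, entries spread evenly over the window would give 0.25 × 1/2 = 12.5% (t1 = 06:00) to 0.625 × 1/2 = 31.25% (t1 = 09:00).

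**Step 3. Direction.** The recorded score is a maximum over the applications rated. Dropping one from a maximum leaves it unchanged or lowers it. It is lowered only if the evening reaction was the worse of the two.

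**Step 4. Would a 24-hour recall close the gap?** Entries on consecutive days can be as far apart as 16:00 on one day and 24:00 on the next, which is 8 + 24 = 32 hours. A 24-hour recall then leaves 32 − 24 = 8 hours uncovered. For example, with entries at 16:30 on Day 1 and 23:00 on Day 2, a 20:00 application on Day 1 is 27 hours old at the second entry and falls outside.

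**The case against.** The strongest reply is that Section 11.5.4 describes the item and does not reproduce it. Section 9.8.4 gives the compliance question verbatim; the tolerability screen text and the training content are not in the documents. If the device already asks about the time since the last entry, there is no gap. The plural reference to applications shows that both were meant to be covered. This stands as a limit: what is shown is a gap in the rule as written, not a measured loss of data.

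Second, a reader might infer that evening reactions go unrecorded altogether. The documents do not support that. Section 13.2 has tolerability queried specifically, Section 11.5.4 allows subject-reported stinging or burning to become an AE even when the investigator suspects no skin reaction, investigators assess tolerability at visits while the subject is on treatment, and the subject rates it again at end of treatment or early termination. But scheduled visits are 4 weeks apart and AE reporting is at the investigator's discretion, so these routes do not replace a daily graded score.

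Third, a reader might infer that a first application in the evening always falls outside the diary. It does not: the diary is open until midnight, and the application is missed only if that day's entry was already submitted. The evening instruction for the HESD also makes very early entries less likely, though it does not exclude them.

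Finally, diary tolerability is not an endpoint in Panel 3, and no comparative analysis is planned. That limits the importance of the gap but does not remove it.

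**Conclusion.** The point holds for the item as described. The entry can precede the second application for any first application after 04:00, and no text assigns the previous evening to the next entry. Reactions to evening applications can then be absent from the diary, and the resulting bias in the weekly summary can only be downward. The effect on the primary endpoint, the number of treatment-emergent AEs, is indirect.

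The size is 0% to 50% of applications. A single figure such as 25% (applications at 08:00 and 20:00, even entry times) might be read as an estimate, but both assumptions come from outside the documents. It also counts applications, not reactions. Nor should the HESD's 24-hour recall be taken as a full solution, given Step 4. The conclusion assumes that the device wording follows Section 11.5.4. A first application is a first exposure to delgocitinib only for former vehicle subjects.

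**What to change.** First compare the device text with Section 11.5.4. If the screen already asks about the time since the last entry, correct the protocol text and nothing else is needed. Otherwise make one of two changes:

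- Word the item as *worst stinging/burning with any trial cream application since your last diary entry*. This leaves no interval between consecutive entries uncovered, even when a day is skipped. Because the item appears only while on treatment, it should be shown once more on the day treatment stops.
- If the device text cannot be changed, instruct subjects in Section 11.3 to complete this item after the evening application. This relies on subjects following the instruction.

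The cost is one line of wording or training, at the price of a small change partway through the data series. Record the date of change. For data already collected, state the limitation beside the Section 14.3.9 summary and, if the device stores entry times, report their distribution.

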#### Reporting in the eCRF

For the subject's assessment of local tolerability at the end-of-treatment/early termination visit, the highest (worst) skin reaction score across treatment area(s) will be recorded in the eCRF.

Page 62 of 121

For the investigator's assessment of local tolerability, it will be reported in the eCRF if the investigator suspects a local skin reaction to be related to application of IMP (yes, no). If the investigator suspects a local skin reaction to be related to application of IMP, the scores in Panel 14 (one score for Scale 1 and zero, one, or multiple scores for Scale 2) will be recorded in the eCRF. The aetiology of the local skin reaction (irritant contact dermatitis caused by IMP, allergic contact dermatitis caused by IMP [requires a positive reaction to IMP patch test, see Section 11.5.4.1], or other [specify]) will be captured in the eCRF and the final diagnosis will be captured as an AE.

Panel 14 Berger and Bowman scoring scales if investigator suspects a local skin reaction related to IMP application

Scale 1				
Skin appearance	Score			
No evidence of irritation	0			
Minimal erythema that is barely perceptible	1			
Definite erythema that is readily visible and minimal oedema or minimal papular response	2			
Erythema and papules	3			
Definite oedema	4			
Erythema, oedema, and papules	5			
Vesicular eruption	6			
Strong reaction spreading beyond the test field	7			

Select the appropriate score (only one score) if a local skin reaction is suspected to be related to application of the IMP.

Scale 2			
Other observations	Letter score		
Slightly glazed appearance	A		
Markedly glazed appearance	В		
Glazing with peeling and cracking	С		
Glazing with fissures	F		
Film of dried serous exudates covering all or part of the patch site	G		
Small petechial erosions and/or scabs	Н		

Other observations (multiple scores allowed) will be recorded if applicable

# 11.5.4.1 IMP patch test procedure

Only if the investigator suspects a local skin reaction related to application of the IMP, an IMP patch test will be performed following scoring according to the Berger and Bowman scales described in Section 11.5.4. The subject's own dispensed delgocitinib cream 20 mg/g as well

Page 63 of 121

as cream vehicle control will be used for the patch test. To avoid contamination, approximately 1 cm of delgocitinib cream should be squeezed out of the tube before performing the IMP patch test. If this is not possible, a new tube of delgocitinib cream will be used (dispensed at the given visit) for the procedure. The trial site staff will apply a small amount of delgocitinib cream and vehicle control to the patch test chambers which will be placed on the subject's upper back and secured with hypoallergenic tape. The patch will be removed after 2 days. The investigator will perform two readings of any apparent patch test reaction 3-4 days and again 5-7 days after applying the patch. The positive patch test reaction will be documented by photography and scored (Panel 15) according to guidelines (39). If the subject has a positive reaction to the IMP patch test, the subject must discontinue treatment with IMP.

Further instructions for the IMP patch test procedure, scoring of the IMP patch test reactions, and photographing any positive patch test reactions will be provided in the laboratory manual.

Panel 15: Patch test reading criteria

Morphology	Patch test reaction score
No reaction	Negative reaction
Faint erythema only	Doubtful reaction
Erythema, infiltration, possibly papules	Weak positive reaction
Erythema, infiltration, papules, vesicles	Strong positive reaction
Intense erythema, infiltrate, coalescing vesicles	Extreme positive reaction
Various morphologies, e.g. soap effect, bulla, necrosis	Irritant reaction

Reading criteria for patch test reactions based on morphology, from Johansen et al. (39).

## Reporting in the eCRF

For the IMP patch test, the date of placement of the IMP patch test, the date of each reading, and the patch test reaction scores will be recorded in the eCRF (negative reaction, doubtful reaction, weak positive reaction, strong positive reaction, extreme positive reaction, or irritant reaction).

The photograph(s) of any positive patch test reactions will be uploaded to the eCRF.

## 11.5.5 Laboratory testing

#### 11.5.5.1 Overview

Blood and urine samples will be collected according to the schedule of trial procedures (Section 4). Laboratory results from the Week 12 and Week 16 visit in the parent trial will be used as screening and baseline results, respectively, in this extension trial.

Page 64 of 121

The evaluations shown in Panel 16 will be performed by the central laboratory.

Panel 16: Clinical laboratory tests performed by the central laboratory

Chemistry	Haematology	Urinalysis 
Sodium	Erythrocytes	Protein
Potassium	Haematocrit	Glucose
Creatinine	Haemoglobin	Ketones
Urea nitrogen	Erythrocyte mean corpuscular	Occult blood
Calcium	volume	Leukocytes
Alkaline phosphatase	Erythrocyte mean corpuscular	Nitrite
Aspartate aminotransferase	haemoglobin concentration	
Alanine aminotransferase	Leukocytes	
Gamma glutamyl transferase	Neutrophils	
Bilirubin 	% neutrophils	
Lactate dehydrogenase	Lymphocytes	
Cholesterol	% lymphocytes	
LDL cholesterol	Monocytes	
HDL cholesterol	% monocytes	
Triglycerides	Eosinophils	
Glucose (non-fasting)	% eosinophils	
Albumin	Basophils	
Protein	% basophils	
	Thrombocytes	

- 1. If bilirubin is above upper limit of normal, direct and indirect bilirubin will also be measured.
- 2. Urine samples will be tested for the listed analytes at trial site (dipstick). It will be at the investigator's discretion to decide whether a urine sample will be sent to the central laboratory for microscopic examination (WBC; RBC; epithelial cells, squamous; epithelial cells, transitional; epithelial cells, renal tubular; hyaline casts; WBC casts; RBC casts; waxy casts; granular casts; calcium oxalate crystals; uric acid crystals; triphosphate crystals; yeast; and bacteria).

**Abbreviations:** HDL = high density lipoprotein; LDL = low density lipoprotein; RBC = red blood cells; WBC = white blood cells

# 11.5.5.2 Investigator evaluation of laboratory samples

## Central laboratory

Chemistry, haematology, and urinalysis (if applicable) will be analysed by a central laboratory which will provide results to the trial sites. Laboratory parameters will be classified as 'low', 'normal', or 'high', depending on whether the value is below, within, or above the reference range, respectively. The investigator must evaluate all results outside the reference range ('clinically significant' or 'not clinically significant') and sign and date the evaluation. The signed and dated version will be filed with the investigator's trial documentation. In case of clinically significant abnormal results, appropriate action, as judged by the investigator, must be taken.

Page 65 of 121

If a screening laboratory result is abnormal and clinically significant, it will be at the investigator's discretion to decide if the subject should be included in the trial.

A laboratory manual will be provided to the trial sites specifying the procedures for collection, processing, storage, and shipment of samples, as well as laboratory contact information specific to this trial.

